4 DEFINING PRESYNCOPE AND SYNCOPES

4.1 Presyncope

For this study, the case definition of presyncope was based on review of the literature, an amended Blood Donations Reactions Inventory (BDRI) which was used in previous studies including the CISA Hydration Study, expert opinion, and prior experience with the CISA hydration study.¹²⁻¹⁴ Although there may be measurable physiological changes with presyncope (e.g., decrease in heart rate or blood pressure), there are no established cut-offs that define presyncope. Therefore, the case definition is based on subjective criteria. The case definition previously used in CISA hydration study to Prevent Post-Vaccination Presyncope (“Water and Vaccines Study”) is outlined below and will be used as the primary definition of presyncope in this study:

Primary definition: *Sudden onset of one or more of the following symptoms (reported as “a little bit”, “somewhat” or “a lot”) or signs during the post-vaccination observation period in the clinic:*

Symptoms

- Feeling like you might “pass out” or faint
- Feeling dizzy, like the room is spinning
- Feeling weak
- Feeling like your face is getting red and warm (or hot), like blushing or flushing
- Noticing any change in your vision, like spots or flickering lights, tunnel vision, or loss of vision
- Experiencing ringing in your ears, decreased hearing, or sounds seem far away
- Feeling lightheaded
- Feeling like your heart is beating fast or hard or pounding
- Feeling hot or sweaty
- Feeling cold or “clammy”
- Feeling like you are breathing fast or hard
- Feeling like you might throw up (nausea)

Signs

- Pallor
- Sweatiness
- Facial flush
- Decreased interactivity (decreased level of arousal or responsiveness)

AND

- Not syncope
- Not due to another cause
- Not clearly present at baseline

In exploratory analyses we will employ two alternate case definitions for presyncope.

Alternate definition 1: *Sudden onset of one or more of the above symptoms (reported as “somewhat” or “a lot”) or signs during the post-vaccination observation period in the clinic.*

Alternate definition 2: *Sudden onset of one or more of the following symptoms limited to feeling like you might pass out, dizziness, weakness, or lightheadedness symptoms (reported as “a little bit”, “somewhat” or “a lot”) or signs during the post-vaccination observation period in the clinic.*

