7.8.1 Blinding

Study staff and subjects will not be blinded to treatment arm assignments.

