7.9 Study Interventions

7.9.1 Buzzy® and Electronic Game Intervention

Participants randomized to Buzzy® and the electronic game will apply or have Buzzy® applied by a member of the study team. Buzzy® XL Healthcare Professional will be applied as described in the package insert on the deltoid vaccination site for 30-60 seconds. Then, the Buzzy® will be moved proximal to the injection site keeping Buzzy's® switch/head toward the brain or spine during injection. The procedures for applying Buzzy® are consistent with the procedures on the package insert (**Appendix A**). If vaccines are given in more than one arm, Buzzy® will be placed on both arms with the assistance of the study coordinator. Buzzy® will be removed from the vaccination site(s) following vaccination. The start and stop time of Buzzy® placement will be recorded. If more than one vaccination is given in a single arm only one Buzzy® device will be applied per package instructions.

For the electronic game, participants will be instructed to select a game from a prepopulated list of games on a tablet provided by the study team. The game will be played for a minimum of 3 to 5 minutes prior to vaccination, throughout the procedure and for a minimum of 1 minute and up to 15 minutes after vaccination.

Although preferable for participants to remain in the same exam room during the post-vaccination observation period, participants may have to shift rooms during the post-vaccination observation period. The participant will be provided with the guidance (derived from the Advisory Committee on Immunization Practices (ACIP) General Best Practices Guidelines for Immunization)²⁶ that they may choose to sit or lie down during the post-vaccination wait period. Movement from room to room or if the patient decides to stand should be noted by the study staff. No instruction will be provided to the participant regarding sitting or standing unless the participant starts to exhibit signs of presyncope.

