7.12 Presyncope and Syncope

At 15 minutes (up to 20 minutes) following vaccination, study participants will complete the BDRI. During the 15 minute (up to 20 minute) observation period, research staff

will also record any observed signs (pallor, sweating, facial flush or decreased interactivity) or spontaneous subject reports of symptoms of witnessed presyncope as described in Section 4.1. Subjects who developed post-vaccination syncope as described in Section 4.2 regardless of presyncope are classified as having syncope. Usual clinical care will be provided to any subject who develops presyncope or syncope.

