##### AND

- Not syncope
- Not due to another cause
- Not clearly present at baseline

In exploratory analyses we will employ two alternate case definitions for presyncope.

Alternate definition 1: Sudden onset of one or more of the above symptoms (reported as “somewhat” or “a lot”) or signs during the post-vaccination observation period in the clinic.

Alternate definition 2: Sudden onset of one or more of the following symptoms limited to feeling like you might pass out, dizziness, weakness, or lightheadedness symptoms (reported as “a little bit”, “somewhat” or “a lot”) or signs during the post-vaccination observation period in the clinic.

b) **Syncope**

Syncope (fainting) that occurs in an otherwise healthy person after receipt of a vaccine or during venipuncture is usually attributed to vasovagal syncope, and may occur alone (simple syncope) or may be associated with tonic-clonic movements (convulsive syncope, anoxic seizure). For the purposes of this study, we have defined syncope as: Any sudden and brief loss of consciousness or postural tone after vaccination from which recovery is spontaneous and is not attributed to another cause (e.g., anaphylaxis). For purposes of this study, cases counted as syncope must occur during the post-vaccination observation period.

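### Decreased interactivity alone can make a primary-endpoint case; unblinded staff judge it by watching while only one arm is assigned a game, and no planned analysis leaves it out

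*Protocol*

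**What the plan says.** **Case definition.** Protocol 4.1, repeated in SAP 4.6, opens with "Sudden onset of one or more of the following symptoms" and then admits signs on the same footing, so a single sign suffices. The fourth of the four signs is "Decreased interactivity (decreased level of arousal or responsiveness"). A case must also meet exclusions, among them "Not due to another cause" and "Not clearly present at baseline".

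**Who rates, and when.** Under Protocol 7.12 research staff "will also record any observed signs (pallor, sweating, facial flush or decreased interactivity") over the 15 (up to 20) minute observation period. Protocol 7.8.1: "Study staff and subjects will not be blinded to treatment arm assignments".

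**What differs between arms.** Protocol 7.9.1 for the intervention arm: "The game will be played for a minimum of 3 to 5 minutes prior to vaccination, throughout the procedure". Play then goes on for at least 1 and at most 15 minutes after the injection. Controls (7.9.2) receive no study game. Neither document says whether they may use their own devices.

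**What is analysed.** SAP 8.1 counts a case found by the modified BDRI or by a witnessed event. The two alternate definitions used for EO 1 raise the symptom threshold or shorten the symptom list, but both retain "or signs during the post-vaccination observation period in the clinic". EO 2 uses the same three definitions.

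**The concern.** Pallor, sweating and flushing look much the same whether or not a child is holding a tablet. Interactivity does not: staff judge it from how the child engages with the surroundings, and the game was chosen (Protocol 1.1) because it demands active involvement. The assigned treatment can therefore change the behaviour being rated, in one arm only, and the raters know the arm. That goes a step beyond ordinary open-label reporting bias.

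The error could run either way. Absorption scored as a sign would add intervention cases and dilute the effect. A real sign put down to the game would remove an intervention case and exaggerate it. A reader of the results could not tell whether either had happened, because every planned definition of the outcome contains this sign.

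**Working it through.** **1. Can the sign make a case alone?** Yes. Protocol 4.1 requires one symptom or one sign, and SAP 8.1 accepts a witnessed event without a positive BDRI.

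**2. Does play overlap the rating window?** Yes. Play lasts 1 to 15 minutes after the injection; signs are recorded over 15 (up to 20) minutes.

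**3. How much do the existing limits remove?** Most of it. Play starts 3 to 5 minutes before the injection, so steady absorption is neither sudden nor new, and it has an obvious other cause. Three gaps remain:
- Baseline is not defined for signs.
- Deciding whether quietness has another cause is left to staff who know the arm, and the question arises mainly in the arm assigned the game.
- The pain contacts in Protocol 7.11, at 1 (up to 3) and 10 (up to 15) minutes, require an answer in both arms but are not linked to rating this sign.

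**4. Reproducing the plan's power.** Inputs from Protocol 8.1: 25% against 12.5%, 160 per arm, two-sided 0.05 chi-square. Pooled rate 0.1875.
- SE under the null: √(2 × 0.1875 × 0.8125 / 160) = 0.04364.
- SE under the alternative: √((0.25 × 0.75 + 0.125 × 0.875) / 160) = 0.04308.
- z = (0.125 − 1.96 × 0.04364) / 0.04308 = 0.916, giving power 82.0%, as stated. Exact binomial enumeration gives 82.4%.

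**5. Illustration of added cases.** The documents give no rate for this sign, so the number k of intervention children counted on it alone is an assumption.
- *p-value:* uncorrected chi-square, 40/160 in control against (20 + k)/160.
- *Power, intervention arm only:* exact enumeration, 25% against (20 + k)/160.
- *Power, both arms:* the same share f = k/140 of non-cases misrated in each arm, that is 0.25 + 0.75f against 0.125 + 0.875f.

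| k | Intervention rate | p at these counts | Power, intervention arm only | Power, both arms alike |
|---|---|---|---|---|
| 0 | 12.5% | 0.0042 | 82.4% | 82.4% |
| 1 | 13.1% | 0.0069 | 77.8% | 80.9% |
| 2 | 13.75% | 0.0109 | 72.6% | 79.4% |
| 3 | 14.4% | 0.0169 | 67.0% | 78.0% |
| 4 | 15.0% | 0.0253 | not tabulated | not tabulated |
| 5 | 15.6% | 0.0371 | not tabulated | not tabulated |
| 6 | 16.25% | 0.0531 | 49.1% | 73.7% |

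The p-value column takes counts exactly at the design rates; the power columns average over chance. Comparing the last two columns, most of the power loss comes from the difference between arms. The row k = 6 (6/140 = 4.3% of intervention non-cases) only marks where significance is lost; nothing in the documents suggests so many.

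**6. Missed cases.** No figure is given. A child missed on this sign changes the endpoint only with no other sign and a negative answer on all 12 BDRI symptoms.

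**The case against.** The strongest reply is that the definition already deals with this. The sign is worded as reduced arousal or responsiveness, and a child actively working a game shows neither. The onset, baseline and other-cause conditions apply to every sign, and a general exclusion need not name each instance. Play after the injection is required for only 1 minute. Every child answers two pain ratings and the BDRI, so an unresponsive child would probably be noticed. Controls may have phones of their own, which would narrow the contrast. SAP 8.1 also names an event form that is not in the supplied text and may carry a rating instruction. Finally, 12 self-reported symptoms, each counting even at the mildest level, will supply most cases.

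Much of this stands. It makes sign-only cases probably few and means that the absence of a rule can be asserted only for the supplied text. It does not remove the attribution decision left to unblinded staff, and it does not supply an analysis without the sign.

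A reader might go further and infer that the game will inflate intervention cases, or that the trial stands to lose its power or its significant result. The documents do not support that. They give no rate for the sign and no direction for the error, and in the illustration one to five added cases leave the design-rate result significant.

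**Conclusion.** The point holds as a cheap improvement, not as a flaw that threatens the trial. In the supplied text, one component of the primary endpoint is judged by passive observation, by staff who know the arm, under conditions that the treatment itself makes different; EO 1 cannot show whether this matters because it keeps the same component.

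The direction and size of any bias are unknown. The illustration rests on the plan's 25% and 12.5%, 160 per arm, and an assumed number of children counted on this sign alone. If the event form already contains a rule for rating interactivity during play, the protocol need only cite it, and only the missing sensitivity analysis remains.

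**What to change.** 1. **Protocol 7.12, both arms.** Rate interactivity by the child's response when spoken to at the contacts already scheduled (pain ratings at 1 to 3 and 10 to 15 minutes, BDRI at 15 to 20 minutes), and also whenever staff suspect the sign between contacts. State that absorption in a game or device with a normal response is not a sign. Using the fixed contacts matters, because a check made only on suspicion would depend on what unblinded staff happen to suspect.
2. **SAP 8.1.** Pre-specify one sensitivity analysis of POM 1 that does not count children, in either arm, whose only qualifying feature is decreased interactivity. The signs are already recorded under 7.12. Fixing the analysis in advance avoids the appearance of selection if the sign is dropped once results are known.

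**Cost.** Brief staff training, a short interruption of play when the sign is suspected, and one extra results row. Genuine sign-only cases are lost from the sensitivity analysis only, and that analysis cannot recover missed cases. The primary and alternate definitions, the game, visit length and sample size stay as they are.

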7.13 Acceptability

At the end of the study visit, we will survey participants about the acceptability of the intervention to which they were assigned. Where appropriate, a Likert scale (strongly agree, agree, neither, disagree, strongly disagree) will be used to assess acceptability responses. Alternately, a yes or no response to survey questions will be solicited.

7.14 Unsolicited SAEs

Administration of vaccine is not itself a study procedure in the study population, and thus vaccine adverse events, including presyncope or syncope, are not considered study related adverse events. If indicated, however, vaccine-related SAEs will be reported to the Vaccine Adverse Event Reporting System (VAERS) in accordance with standard procedures. Information about such events will be included in the study data as noted on the VAERS website (<https://VAERS.hhs.gov>).

All serious adverse events (SAEs) occurring during the period of study participation will be reported to the IRBs overseeing this study and to the CDC within 24 hours of study staff awareness of the event. Given the short duration of study participation and nature of the study, SAEs would not be expected to occur in this study.

An SAE is defined as an AE that meets one of the following conditions:

- Results in death during the period of protocol-defined surveillance
- Is life-threatening (defined as immediate risk of death at the time of the event)
- Requires inpatient hospitalization during the period of protocol-defined surveillance or results in prolongation of existing inpatient hospitalization (other than routine hospital admission for labor & delivery).
- Results in congenital anomaly or birth defect
- Results in a persistent or significant disability/incapacity
- Any other important medical event that may not result in death, be life threatening, or require hospitalization, may be considered an SAE when, based upon appropriate medical judgment, the event may jeopardize the subject and may require medical or surgical intervention to prevent one of the outcomes listed above. Examples of such medical events include allergic bronchospasm requiring intensive treatment in an emergency room or at home, blood dyscrasias or convulsions that do not result in inpatient hospitalization, or the development of drug dependency or drug abuse.

8 STATISTICAL CONSIDERATIONS

Data will be handled according to the Duke Vaccine and Trials Unit SOP (DVTU M010) and captured on paper CRFs and entered into the REDCap database. All data for this study will reside on a secure Duke server maintained by Duke Health Technology Solutions (DHTS). A database will be developed and a dataset without personal

identifiers will be made available to the CDC for analysis purpose. All analyses will be performed using SAS version 9.4.

8.1 Sample Size and Power Estimation

The study has approximately 82.0% power to reject the null hypothesis of no difference in the proportion of adolescents with presyncope or syncope after vaccination in the intervention (vibration and cool pack device [Buzzy®] and an electronic game) group compared to the control (usual care) group based on a two-side alpha 0.05 chi-square test with N=160 per group. This assumes that the proportion of adolescents with presyncope or syncope after vaccination will be 25% in the control group and 2-fold lower (12.5%) in the intervention group.¹⁵ This assumption is based on a review of the literature and expert opinion. We plan to enroll approximately 340 adolescents for this study with the assumption of a 5% drop out rate, thus providing at least 160 subjects per group to have approximately 82% power.

8.2 Analysis Plan

8.2.1 Study Populations

The study will enroll adolescents, female and male, ages 10-14 years, receiving at least one ACIP recommended vaccine administered intramuscularly. Participants will be randomized into either of the two groups: intervention (vibration and cool pack device [Buzzy®] and an electronic game) or the control (usual care).

There will be two study populations used for data analysis in this study. These are defined below:

- Modified Intent-to-treat (MITT) population: is defined as those subjects who are enrolled, randomized into the study, and received an intramuscular vaccine.
- Per-protocol population: is defined as those subjects who are randomized, have received at least one dose of an intramuscularly administered vaccine, have completed all study procedures, and have no protocol violations that are likely to affect the objectives.

The primary and exploratory objective analyses will be performed in the MITT and Per-protocol populations, or only the MITT population if no subject is excluded from the per protocol population. No adjustments will be made to the alpha level (two-sided alpha=0.05) for the study objectives described below.

8.2.2 Descriptive Statistics

Descriptive analyses will be conducted for demographic variables and for baseline characteristics (e.g., fatigue, hunger, thirst, needle fear and phobia, and an anxiety rating scale score). Continuous variables will be summarized with standard descriptive statistics including means, medians, 95% CI, and standard deviations. Categorical variables will be summarized with frequencies and percentages. Ninety-five percent confidence intervals will be provided for descriptive statistics, as warranted. The descriptive statistics will be analyzed in the MITT and Per-protocol populations.

8.2.3 Primary Objective (PO 1):

The primary objective is to assess if simultaneous use of a vibration and cool pack device (Buzzy®) and an electronic game before and during intramuscular vaccination will reduce risk for presyncope or syncope after vaccination in adolescents. The proportion of adolescents with presyncope or syncope after vaccination will be compared between the control and intervention groups using a chi-square test.

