Post-vaccination vasovagal syncope and associated injuries, as well as risk for recurrent symptoms and related interference in functioning, are a public health concern that should be addressed with evidence-based preventive interventions. Although post-vaccination presyncope does not always lead to syncope, it is more common than syncope, and both are vasovagally-mediated,^{11,14} so presyncope is appropriate for use as a surrogate for syncope in prevention research. Presyncope has been used as a surrogate for syncope in syncope prevention studies in the blood donation literature. Also, CDC supported a previous post-vaccination syncope prevention study at Duke and Boston University using presyncope as a surrogate endpoint for syncope.¹⁵

Predictors of Vasovagal Syncope

The efficiency of primary prevention of vasovagal syncope could be improved if preventive interventions could be targeted at those at greatest risk. Unfortunately, predicting risk of syncope is difficult. In blood donors, for example, pre-donation blood pressure was not associated with risk of syncope and a pre-donation elevated pulse rate has inconsistently been associated with risk of syncope,¹⁶⁻¹⁸ and the best predictor, anxiety, demonstrated only a modest association.¹⁹ Due to the challenge of accurately predicting risk, any preventive intervention would likely have to be broadly applied.

Published systematic reviews and meta-analyses of interventions to prevent blood donation-related vasovagal symptoms and syncope in young donors suggest that risk factors for post-vaccination and post-blood-donation vasovagal (not volume depletion) syncope include: 1) younger (adolescents) and first time donors; 2) anxiety; 3) needle phobia; and 4) prior history of syncope from needle-related event(s).^{6,11,14,16,17,20-24} Some publications also cite increases in syncope among females;^{11,16,17,21,23-25} and among those with a prior history of fainting or feeling faint (due to any reason).^{17,22,23} Blood donation literature also suggests that vasovagal syncope is more common among Caucasians as compared to African-Americans,^{17,24} and in persons with lower body mass index (BMI) as compared to greater BMI.¹⁶

Current Recommendations Related to Post-Vaccination Syncope

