Unlike the blood donation literature, there are limited data on effective strategies to prevent post-vaccination vasovagal syncope. Only one randomized clinical trial has assessed an intervention to prevent post-vaccination syncope. A recent Clinical Immunization Safety Assessment (CISA) randomized clinical trial (Kemper et al, ClinicalTrials.gov NCT02353390)³⁰ assessed the effectiveness of pre-vaccination hydration with water to prevent presyncope (used as a surrogate for syncope). Drinking some water before vaccination was not effective in preventing presyncope and by extension syncope, prompting CISA to plan evaluations of other simple interventions that could be used in busy clinical settings. The hydration study demonstrated the following as risk factors for post-vaccination presyncope among subjects 11-21 years: receiving more than one injectable vaccine; age younger than 15 years; having higher pre-

vaccination anxiety levels; history of passing out or nearly passing out after a “shot” or blood draw within the preceding 5 years, and having higher levels of pain after vaccination (presumed injection-site pain).¹⁵ These predictors may inform other strategies for preventing pre-syncope such as reducing immediate pain after vaccination in addition to promoting relaxation and reducing anxiety around the time of vaccination.

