7 STUDY SCHEDULE, PROCEDURES, & EVALUATIONS

7.1 Schedule of Events

Adolescents meeting the proposed eligibility criteria will be recruited and if enrolled the subject could spend up to two hours in the clinic. Written permission for the adolescent to participate will be obtained from parent(s)/guardian(s) prior to conducting any study procedures. Written or verbal assent, depending on the age of the adolescent, will also be obtained. **Table 1** describes the proposed schedule of study visits.

Table 1: Schedule of Study Events:

Procedure	Pre-Vaccination Day 1	Vaccination Day 1	Post-Vaccination Day 1
Informed consent / Assent	X		
Inclusion/Exclusion	X		
Demographics	X		
Medical history	X		
Concomitant medications	X		
Beverage and food intake assessment on day of vaccination	X		
PROMIS Pediatric Anxiety Short Form	X		
Needle phobia assessment	X		
State Anxiety assessment	X		X ¹ (20 minutes)
Record/obtain physical measures (height and weight) and vital signs (blood pressure and pulse and baseline pain assessment done per usual care)	X		
Randomization	X		

Simultaneous Buzzy® and electronic game intervention or usual care	X		
Administer vaccines (not a study procedure)		X	
Injection site pain assessment			X (within 1-3 and at 10 minutes)
Presyncope symptoms assessment			X (15 minutes)
Acceptability Assessment			X (20 minutes)

¹ Complete prior to acceptability assessment

Visit 1, Study Day 1 Clinic Visit Prevaccination Assessments

- Obtain parent(s)/guardian(s) permission by written informed consent
- Review and confirm study eligibility (Section 4.1 and 4.2)
- Obtain medical history
- Obtain demographic data
- Obtain concomitant medication use within one week of enrollment
- Record height and weight and vital signs (blood pressure and pulse) from the medical record. Obtain measures if not already taken and recorded at clinic intake. Record baseline pain assessment if determined as part of clinical care
- Complete beverage and food intake assessment for the day of vaccination
- Complete the needle phobia assessment
- Complete the general anxiety assessment and the state anxiety assessment
- Randomize study participant to one of the two study arms
- Administer assigned study intervention if randomized to that group

Visit 1, Study Day 1 Clinic Visit Vaccination

- Vaccines administered by clinic staff (Not a study procedure)
- Vaccines administered as usual care will be recorded by study team

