7.3 Overview of Study Assessments

Table 2 briefly outlines factors of interest that are potentially associated with pre-syncope or syncope. A more complete description of some of the specific measurements and questionnaires follows the table.

Table 2: Factors of Interest that are Possibly Related with Pre-syncope or Syncope		
Domains of Interest	Source of Information	Information obtained
Demographics	Participant and/or parent report	Participant's gender, age, race, ethnicity
Underlying Health (Chronic or acute illness)	Participant and/or parent report Review of medical record	Medical history information: (history of pre-syncope, syncope, cardiac conditions, seizures, hypoglycemia, diabetes, prescription and over-the counter medications in preceding week, supplements in preceding week)
Physical Measures	Height, weight, pulse rate and blood pressure measurements (from medical record if obtained or measured, otherwise measured by study staff) Pain at baseline (from medical record)	Height, weight and calculated BMI Pulse rate and blood pressure Pain assessment at baseline
Fatigue/ tiredness	Participant response	Estimated hours of sleep the previous night Feeling tired
Hunger	Participant response	Last food eaten Hunger estimation
Thirst	Participant response	Time/type of last beverage consumed prior to vaccination

		Quantification of last beverage Thirst estimation
Needle-related fear	Participant response	Needle phobia questionnaire Global question about fear of injections
Anxiety	Participant response	PROMIS Pediatric Anxiety Short Form pre-vaccination, and state anxiety questionnaire pre- and post-vaccination
Number of Injections	Medical record review (EHR/electronic health record or State Immunization Registry)	Number / name / site of injections administered in clinic
Pain	Participant response	Wong-Baker Faces Pain Scale score post vaccination
Past history of presyncope or syncope after injection or blood draw during the past 5 years	Participant response	Questions about past history of almost fainting or fainting and circumstance

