7.8 Randomization

Participants will be randomized (1:1) to receive either Buzzy® and electronic game or the control using a permuted block randomization scheme. A minimum of 170 participants will be enrolled in the intervention group and 170 in the control group. The project statistician at Duke University will generate randomization schemes, which will be uploaded to REDCap. The randomization schedule will not be available to the study staff, so the next randomization allocation will not be known before randomization occurs. Following confirmation of study eligibility criteria during Visit 1, participant randomization will be through REDCap with treatment allocation recorded on the CRF.

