## 8 Analysis of study objectives

### 8.1 Primary Objective (PO1)

To assess if simultaneous use of a vibration and cool pack device (Buzzy®) and an electronic game before and during intramuscular vaccination will reduce risk for presyncope or syncope after vaccination in adolescents. This information is collected in CRF forms: “Buzzy® Form”, “Electronic Game Form”, “Presyncope or Syncope Form (EVENT FORM)”, and “Post Vaccination Questions” (Modified BDRI (PostVax)). The proportion of adolescents with presyncope or syncope as determined by the modified BDRI or witnessed presyncope or syncope after vaccination will be compared between the control and intervention groups using a chi-square test.

- *Research hypothesis: The Buzzy® and electronic game intervention will be at least 50% effective at reducing risk for post-vaccination presyncope or syncope compared with control.*  
This objective will be assessed using a chi-square test with the alpha level set at 0.05 (2-sided).

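### The primary chi-square uses no baseline information; pre-specified adjustment for two predictors the protocol names and collects would add some precision at little cost

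*Protocol*

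**What the plan says.** Protocol 8.2.3 gives the whole primary analysis in one sentence: "The proportion of adolescents with presyncope or syncope after vaccination will be compared between the control and intervention groups using a chi-square test". SAP 8.1 repeats that the proportions "will be compared between the control and intervention groups using a chi-square test", at two-sided 0.05. Neither section mentions a covariate. Protocol 7.8 and SAP 4.4 allocate 1:1 "using a permuted block randomization scheme" and name no stratification factor.

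Protocol 1.1 lists risk factors for presyncope from the earlier hydration trial. Two of them are pre-"vaccination anxiety levels; history of passing out or nearly passing out after a" shot or blood draw in the preceding five years. Protocol 4.1 adopts that trial's case definition as the primary one here. On strength, Protocol 1.1 says of blood donors only that "the best predictor, anxiety, demonstrated only a modest association".

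Both factors are collected. Before the randomisation step, Protocol 7.1 lists: "Complete the general anxiety assessment and the state anxiety assessment". Table 2 in Protocol 7.3 lists "Past history of presyncope or syncope after injection or blood draw during the past 5 years" as a participant-reported item.

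**The concern.** Neither the design nor the primary analysis uses prognostic information that the protocol itself identifies. About 60 events are expected, so some precision may be given up. If the arms differ visibly on anxiety or fainting history, any adjustment would have to be chosen after the fact, in an open-label trial with a largely self-reported outcome.

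Nothing else in the plan fills the gap:
- SAP 7.1 tabulates generalised anxiety and syncope history by arm, but plans no adjusted effect.
- EO 2 is a risk-factor model with an open-ended covariate list. The list includes pain, which is measured after vaccination and which the intervention is meant to change.
- Covariate adjustment of a treatment comparison is offered only as an option, for the pain proportions under SO 2.

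**Working it through.** **1. The plan's own figure.** Inputs from Protocol 8.1: 25% v 12.5%, n = 160 per arm, two-sided 0.05.

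- Pooled rate 0.1875; SE under the null = √(2 × 0.1875 × 0.8125 / 160) = 0.04364.
- SE under the alternative = √((0.25 × 0.75 + 0.125 × 0.875) / 160) = 0.04308.
- Power = Φ[(0.125 − 1.96 × 0.04364) / 0.04308] = Φ(0.916) = 82.0%, as stated.
- With the unpooled SE throughout: Φ(0.125 / 0.04308 − 1.96) = 82.7%. So about 0.7 points of any gain below come from the form of the SE, not from the covariates.

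**2. Usable covariates.** The hydration-trial list also includes age under 15, number of injections and pain.
- Age under 15 is constant when eligibility is 10 to 14 years.
- Injections are recorded as given: "Number / name / site of injections administered in clinic".
- Pain is post-randomisation.

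That leaves anxiety and needle-related history. Expected events are 160 × (0.25 + 0.125) = 60, or 20 for each of the three non-intercept terms (arm, anxiety, history).

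**3. Gain from adjustment.** The documents give no strength of association, so the odds ratios (OR) and a 10% prevalence of history are assumptions. There were 20,000 simulated trials per scenario, in permuted blocks of 4 (assumed), with intercepts set to give marginal risks of 25% and 12.5%. The data also depended on number of injections (60% with two or more; OR 1.3, 1.7, 2.5), which the fitted model omitted. The adjusted analysis was a logistic model with arm, anxiety and history, standardised to a risk difference with an influence-function SE.

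| Scenario | OR per SD anxiety | OR history | Chi-square power | Adjusted power | Gain | Gain less 0.7 | Variance change | Equivalent extra participants |
|---|---|---|---|---|---|---|---|---|
| Weak | 1.3 | 1.5 | 82.4% | 83.4% | 1.0 | 0.3 | −0.5% | 320/0.995 − 320 ≈ 2 |
| Moderate | 1.6 | 2.5 | 82.7% | 84.8% | 2.1 | 1.4 | −3.8% | 320/0.962 − 320 ≈ 13 |
| Strong | 2.2 | 4 | 82.6% | 86.9% | 4.3 | 3.6 | −9.9% | 320/0.901 − 320 ≈ 35 |

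- Moderate case with history at 3% or 20% (8,000 trials): total gain 1.5 or 2.8 points.
- Adding number of injections, if recorded before allocation: total gains 1.1, 2.5 and 5.1 points.
- Covariates with no predictive value: variance up about 0.6%.
- Null (25% v 25%): chi-square rejects in 4.9% to 5.3% of trials, the adjusted test in 4.9% to 5.3% (up to 5.5% in a 10,000-trial run). Coverage of the adjusted interval: 94.5% to 95.1%.

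A separate simulation (4,000 trials per scenario, slightly different odds ratios) agrees: 82.5% to 83.4% at OR 1.3 and 1.5, 82.8% to 84.0% at 1.5 and 2, and 81.0% to 85.1% at 2 and 3.

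**4. Chance imbalance.** The between-arm difference in mean anxiety has SD √(2/160) = 0.112 in units of the anxiety SD. P(gap of 0.2 SD or more) = 2[1 − Φ(0.2/0.112)] = 7.4%. A 0.2 SD gap moves the unadjusted risk difference by 0.8, 1.3 or 2.0 points in the three scenarios, against a planned 12.5. It moves the adjusted estimate by about 0.

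**The case against.** The case for leaving the plan alone is reasonable. The chi-square is valid, the trial meets its planned power, and unstratified permuted blocks are legitimate. The only statement of strength in the documents is that the association is modest, which points to the weak or moderate rows, where the covariates add 0.3 to 1.4 points. Chance imbalance is already reflected in the chi-square's variance, so that argument partly repeats the precision argument, and an open label does not make imbalance more likely. The adjusted test can also be slightly liberal: in one null run of 20,000 trials it rejected in 5.35% against 5.1% in the weak case. A supportive adjusted analysis would meet the post hoc concern without replacing the primary test.

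Much of this stands as to size. The gain may be close to nil, and the strong row has no support in the documents. Two practical points also stand:
- If history is as rare as 3%, that subgroup has no events, or only events, in about 4% (moderate) to 9% (weak) of trials. The fallback must cover this.
- The power text and EO 1 refer to the chi-square and would need matching words.

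The change is still worthwhile. The modest association was seen in blood donors, whereas the hydration-trial list comes from people of 11 to 21 years under the same presyncope definition. The loss if the covariates fail is well under 1% in variance.

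**Conclusion.** The concern holds as a low-cost improvement to a valid analysis. Adjustment would raise power from about 82.5% to between 83.4% and 86.9% under the assumed associations, and the lower half of that range is the more plausible. The downside is a variance increase of about 0.6% if the covariates predict nothing, with type I error staying near 5%. These figures rest on assumed odds ratios, an assumed 10% prevalence of history and an assumed block size. The state anxiety form was designed for this study (Protocol 7.7), so its predictive value is not documented. The fix also depends on the history questions being asked before allocation. Table 1 places medical history before randomisation, but Table 2 gives no timing for the history item.

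**What to change.** In Protocol 8.2.3 and SAP 8.1, before outcomes are examined by arm:

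- Make the primary analysis a logistic model with arm, pre-vaccination state anxiety score, and needle-related faint or near-faint in the past five years (yes/no).
- Standardise it over the mITT sample to give the marginal risk difference and relative risk with robust 95% confidence intervals. The hypothesis of at least 50% effectiveness is on the risk scale, and the current text specifies a test with no effect estimate.
- Keep the chi-square as supportive analysis, and as the fallback if the model does not converge or the history group has no events or only events.
- Fill missing baseline values with the overall mean or most frequent category, ignoring arm.
- Exclude post-vaccination pain. Add number of injections (1 v 2 or more) only if the planned number is recorded before allocation. Age within 10 to 14 is optional.
- Confirm that the history questions are completed before randomisation.

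The cost is wording in these two sections, a line in the power text (Protocol 8.1, SAP 4.3) and in EO 1 so that methods match or the difference is stated, and short SAS code. The core model needs no new data; including injections needs one new pre-allocation field.
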